5.2.4 Electrocardiogram

The 12-lead ECGs (I, II, III, aVR, aVL, aVF, V1-V6) will be recorded after the patients have rested for at least 5 minutes in a supine position. Electrode placement will be performed according to the method of Wilson, Goldberger and Einthoven. The ECGs will be evaluated by the study physician investigator or designee. ECGs may be repeated for quality reasons and the repeat tracing may be used for analysis. Additional ECGs may be collected by the investigator for safety reasons. Abnormal ECG recordings will be noted, and clinically relevant abnormal findings will be reported as AEs by the investigator. Any ECG abnormalities will be carefully monitored and if necessary medically treated.

ECG recordings will be obtained from roll-over visit and every 24 weeks, until study end including Extended EOT visit and Extended EOS visit

ECG measurements should, if possible, always precede blood sampling to avoid impact of sampling on the ECG results.

Signed and dated printouts of either ECG tracings or electronic ECG reports will be kept in the subject's/patient's medical file.

5.2.5 Assessment of other safety parameters

Vital signs

Vital signs include blood pressure (BP), pulse rate (PR), respiratory rate (RR), and oral or tympanic body temperature.

Proprietary confidential information.

© 2018 Boehringer Ingelheim International GmbH or one or more of its affiliated companies. All rights reserved.

This document may not - in full or in part - be passed on, reproduced, published or otherwise used without prior written permission.

Systolic and diastolic BP as well as PR (by palpation, counted for 1 minute) will be measured after 5 minutes of rest in the supine position. (cf. [Flow Chart](#) for time points).

Measurements of vital signs should, if possible, always precede blood sampling to avoid impact of sampling on the results of vital signs.

Medical examination

Complete physical examination will include vital sign assessment and general appearance as well as evaluation of all organ systems (eyes, ears, nose, mouth, and throat, neck, respiratory, cardiovascular, chest, gastrointestinal, lymphatic, musculoskeletal, skin, neurologic and psychiatric). Targeted physical examination will include vital sign assessment and evaluation of organ systems associated with AE(s) symptoms or laboratory abnormalities.

The medical examination carried out at the initial roll-over visit, will include documentation of patient information, informed consent, demographics including weight and waist circumference, smoking and alcohol history, relevant medical history and concomitant medication, review of inclusion/exclusion criteria, review of vital signs, 12-lead ECG and laboratory, and a complete physical examination.

Local tolerability

Local tolerability at the administration site of the subcutaneous injection will be assessed by the investigator according to “swelling”, “induration”, “heat”, “redness”, “pain”, or “other findings”.

5.3 OTHER

5.3.1 Other endpoint(s)

Not applicable

5.3.2 Other assessment(s)

Not applicable

5.3.3 Pharmacogenomic evaluation

No pharmacogenetic samples will be collected in this study, as those samples will be available from the preceding trial.

5.4 APPROPRIATENESS OF MEASUREMENTS

The majority of measurements performed during this trial are standard measurements and will be performed in order to monitor safety aspects and to determine efficacy, PK and PD parameters in an appropriate way.

The scheduled measurements are appropriate to see drug induced changes in vital signs, standard laboratory values and ECG. These safety measurements standard and accepted for

Proprietary confidential information.

© 2018 Boehringer Ingelheim International GmbH or one or more of its affiliated companies. All rights reserved.

This document may not - in full or in part - be passed on, reproduced, published or otherwise used without prior written permission.

evaluation of safety and tolerability of an s.c. drug, and they are widely used in this kind of study.

The PK parameters and measurements outlined in Section 5.5 are generally used as measurements to assess drug exposure.

The efficacy endpoints are standard for assessment of patients with moderate to severe psoriasis. In addition, a number of exploratory PD measures (biomarkers) are also incorporated in this CTP. As these biomarkers have not been validated as prognostic measures, they may be analysed selectively and may not be included in the clinical trial report.

5.5 DRUG CONCENTRATION MEASUREMENTS AND PHARMACOKINETICS

Time points for dosing, PK and ADA sampling are listed in [Flow Chart](#). Date and exact clock time of administration as well as pharmacokinetic and ADA sampling time points will be recorded. They will be documented in the CRFs by the medical personnel.

5.5.1 Pharmacokinetic endpoint(s)

PK samples will serve to determine the following endpoints:

- steady state trough concentrations of BI 655066.

Individual concentration-time data with descriptive statistics for trough concentrations will be presented in the CTR. If deemed necessary, further appropriate pharmacokinetic parameters might be calculated.

Pharmacokinetic data may additionally be analysed using population pharmacokinetic approach. For this purpose data may also be combined with data from other trials. Modelling activities will be planned and documented separately.

5.5.2 Methods of sample collection

5.5.2.1 Plasma sampling for pharmacokinetic analysis

For the quantification of analyte plasma concentrations, approximately 2.5 mL of blood will be taken from a forearm vein into a K₃EDTA (ethylenediaminetetraacetic acid) anticoagulant blood-drawing tube at the time points listed in Flow Chart under PK sampling.

Mix the K₃EDTA-anticoagulated blood samples gently and place on ice until centrifugation at approximately +4°C. The blood should be centrifuged to produce plasma as soon as possible after collection, but not later than 30 minutes after withdrawal. Centrifugation will last for approximately 10 minutes (at 2000 x g to 4000 x g) at approximately +4°C. Two aliquots of EDTA plasma samples will be obtained in two polypropylene cryotubes. The two aliquots should contain approximately 0.5 mL of plasma each. Until shipment on dry ice to the analytical laboratory, the plasma samples will be stored at -20°C or below at the clinical

Proprietary confidential information.

© 2018 Boehringer Ingelheim International GmbH or one or more of its affiliated companies. All rights reserved.

This document may not - in full or in part - be passed on, reproduced, published or otherwise used without prior written permission.

site and at the analytical laboratory until analysis. Both aliquots will be shipped (in separate shipments) to the assay laboratory for the determination of BI 655066. Both aliquots will be stored until the finalization of the clinical trial report and permission for sample disposal is provided. Samples will be shipped on dry ice sufficient for 3 days transit.

5.5.2.2 Plasma sampling for assessment of anti-drug antibody

For the assessment of anti-drug antibody, approximately 2.5 mL of blood will be taken from a forearm vein into a K₃EDTA anticoagulant blood-drawing tube at the time points listed in the [Flow Chart](#) under ADA.

Mix the K₃EDTA-anticoagulated blood samples gently and place on ice until centrifugation at approximately +4°C. The blood should be centrifuged to produce plasma as soon as possible after collection, but not later than 30 minutes after withdrawal. Centrifugation will last for approximately 10 minutes (at 2000 x g to 4000 x g) at approximately +4°C. Two aliquots of EDTA plasma samples will be obtained in two polypropylene cryotubes. Both aliquots should contain approximately 0.5 mL of plasma each. Until shipment on dry ice to the analytical laboratory, the plasma samples will be stored at -20°C or below at the clinical site and at the analytical laboratory until analysis. Both aliquots will be shipped (in separate shipments) to the assay laboratory for the assessment of potential ADA to BI 655066. The ADA sample aliquots will be banked for possible/ additional ADA characterization in the future. Samples will be shipped on dry ice sufficient for 3 days transit.

5.5.3 Analytical determinations

BI 655066 concentrations will be determined by a validated Enzyme Linked Immunosorbent Assay (ELISA).

The presence of ADA to BI 655066 will be assessed via a tiered approach using a validated electrochemiluminescence assay (screening, confirmatory, and titration analysis as appropriate). Samples that are confirmed positive will then be characterized in a validated neutralizing antibody (NAb) assay.

5.6 BIOMARKER(S)

Biomarkers associated with psoriatic disease and the IL-23 pathway will be assessed in plasma and serum from psoriasis patients, post treatment with BI 655066.

Blood samples (serum and plasma) will be collected at time points indicated in Flow Chart for the analysis of biomarkers. After completion of the study these samples may be used for not yet specified non-genetic biomarker analyses associated with autoimmune diseases as well as method development and evaluation. Samples will be stored for a maximum of 3 years (under consideration of local legislation) upon signature of the final study report.

5.6.1 Endpoints based on biomarker(s)

Serum and plasma will be collected to assess changes in protein levels of disease specific markers such as but not limited to β defensin 2, neutrophil gelatinase associated lipocalin (NGAL), and S-100 proteins (A7, A8, A12) post treatment with BI 655066. These biomarkers are considered exploratory biomarkers and respective assays will need to be qualified to meet the required performance criteria.

5.6.2 Methods of sample collection

For the assessment of soluble protein biomarkers in serum, approximately 8 ml of blood will be collected from a forearm vein in a serum separation tube at time points indicated in the [Flow Chart](#). The blood will be thoroughly mixed with clotting activation agent by inverting the tube not less than five times and will be allowed to clot for 30 minutes with the tube standing upright. The tube is then centrifuged at 1500 to 2000 x g for 15 minutes until clot and serum are separated by a well formed barrier. The serum will then be aliquoted in at least 6 aliquots (in polypropylene tubes) of at least 500 μ l and should be frozen immediately at -20°C or below until shipment on dry ice to the analytical laboratory.

For the assessment of soluble protein biomarkers in plasma, approximately 8 ml of blood will be collected from a forearm vein in a potassium -EDTA (ethylenediaminetetraacetic acid)- anticoagulant blood drawing tube at the time points indicated in the Flow Chart. Tube content will be mixed immediately by gently inverting the tube at least 8 to 10 times and tube will then be transferred into an ice bath until centrifugation. The EDTA-anticoagulated blood sample will be centrifuged within 30 minutes after collection (intermittent storage in ice water or on ice). Centrifugation will last for about 10 minutes at 2000-4000 x g at 4-8°C until cells and plasma are well separated. After centrifugation, the EDTA plasma will be aliquoted in at least 6 aliquots (in polypropylene tubes) of at least 500 μ l and will be frozen immediately at -20°C or below.

5.6.3 Analytical determinations

Characteristics of the analytical methods for the analysis of serum and plasma biomarkers will be given in detail in the clinical trial report or in an accompanying technical/biomarker report.

5.7 PHARMACODYNAMICS

Serum and plasma will be collected to assess changes in the levels of disease specific markers such as but not limited to β defensin 2, neutrophil gelatinase associated lipocalin (NGAL), and S-100 proteins (A7, A8, A12).

5.7.1 Pharmacodynamic endpoints

Cf. [section 5.6.1](#).

5.7.2 Methods of sample collection

Cf. [section 5.6.2](#).

5.8 PHARMACOKINETIC - PHARMACODYNAMIC RELATIONSHIP

No formal analysis of pharmacokinetic/pharmacodynamic relationships is planned.

If the data suggest a pharmacokinetic/pharmacodynamic relationship of special parameters, e.g. PASI, a detailed analysis may be performed.

Correlation between drug concentration and response may be made if adequate data are available. In addition, exploratory correlations may also be made between drug concentration and AEs.

Data may also be used to develop pharmacokinetic/pharmacodynamic models using nonlinear mixed effect modelling techniques, if feasible. For this purpose data may also be combined with data from other trials. Modelling activities will be planned and documented separately according to internal and external guidelines and SOP.

Proprietary confidential information.

© 2018 Boehringer Ingelheim International GmbH or one or more of its affiliated companies. All rights reserved.

This document may not - in full or in part - be passed on, reproduced, published or otherwise used without prior written permission.

6. INVESTIGATIONAL PLAN

6.1 VISIT SCHEDULE

All subjects have to adhere to the visit schedule as specified in [Flow Chart](#). Any missed appointments should be re-scheduled as soon as possible. If any visit has to be rescheduled, subsequent visits should follow the original visit date scheduled. The investigator/sponsor could decide to arrange an unscheduled visit if deemed necessary (e.g. for safety follow-up reasons).

For detailed description of the trial procedures, please refer to [Flow Chart](#).

In general, if several measurements including venipuncture are scheduled for the same point of time, venipuncture should, if possible, be the last of the measurements due to its mild discomfort to the patient and possible influence on physiologic parameters.

6.2 DETAILS OF TRIAL PROCEDURES AT SELECTED VISITS

6.2.1 Screening and run-in period(s)

Patients in the 1311.2 trial that fulfil the criteria for roll over, either by response < PASI₅₀ between week 24 and week 44, or completing the entire preceding trial reaching week 48 according to protocol, will be asked to participate in this open label extension trial. Upon their agreement, they will immediately enter the treatment phase. Therefore, no screening or run-in procedures are defined in this protocol.

6.2.2 Treatment period(s)

6.2.2.1 Rollover visit - Extended visit 1

After the approval of this protocol amendment in each respective country, all patients will follow [Flow Chart](#) (Extended dosing period) and receive 90mg BI 655066 subcutaneously at their Extended visit 1 (EV1). From EV1 onwards, BI655066 will be administered subcutaneously every 12 weeks during the trial. At EV2, if there is inadequate response, defined as <PASI₉₀, the dose should be increased to 180mg for the remainder of the trial.

For ongoing patients from under the previous amendment (Pre-Extended Dosing Period, [see Figure 3.1.3](#)), EV1 should be conducted at the following time points:

1. For ongoing patients with ≥ 12 weeks since the EOT visit: Conduct EV1 as soon as possible
2. For ongoing patients still undergoing treatment or with <12 weeks since the EOT visit: Conduct EV1 at the time of the next scheduled treatment or follow up visit (note: EV1 should not be conducted at the time point of Visit 2 under the previous protocol, patients with Visit 2 as their next scheduled visit should have their EV1 replacing their Visit 3 instead)

Patients completing their EOS of 1311.2 and rolling over after approval of this protocol amendment, is immediately entering the Extended dosing period at EV1 of this trial. Eligible patients from 1311.2 who sign the informed consent for trial 1311.13, should preferably have Extended visit 1 of trial 1311.13 performed on the same day as the last visit in 1311.2, or within an interim period of up to 6 weeks thereafter.

Assessments performed at EOS in the previous trial do not have to be repeated at Extended visit 1 in this trial, if performed as combined visits. If EV1 is performed as a separate visit to 1311.2 EOS, all EV1 assessments should be performed, but specific assessments are only required at EV1 for patients that are having EV1 as their first 1311.13 visit, see Flow Chart for further instructions.

Written informed consent in accordance with GCP and local legislation must be obtained prior to any study related procedure taking place. If not performed as combined visits, informed consent must therefore be signed before the roll-over visit due to lab sampling fasting at EV1 in trial 1311.13.

Review of the following inclusion/exclusion criteria will be based on the last available lab result from previous trial, at the time of roll-over, and needs to be re-assessed as soon as 1311.2 EOS/1311.13 roll-over visit results are available:

- Inclusion criteria 3 (Negative serum β -Human Chorionic Gonadotropin (β -HCG))
Exclusion criteria 8 (Any clinically significant laboratory abnormalities)

Check consistency in medical history with the data obtained at visit 1 of the previous trial. All changes in medical history must be documented as adverse events and will be followed up as such during this trial.

Re-record ongoing adverse events/concomitant medications from the previous trial and record any adverse events/concomitant medications that may have started between the two trials, in the event that the 6 week time-window between trials was used.

All patients will be administered 90 mg BI 655066 s.c. at Extended visit 1.

6.2.2.2 Extended Dosing Period

After 12 weeks, if there is a lack of response, defined as response below PASI₉₀ at Extended visit 2, the dose should be increased to 180 mg, and 180 mg dosing will occur every 12 weeks until Extended EOT.

Self-administered patient questionnaire (DLQI) should be completed by the patient before any other visit assessments or treatments.

For detailed description of the trial procedures, please refer to [Flow Chart](#).

6.2.3 End of trial and Extended follow-up period

Trial 1311.13 is an open label extension trial which was set up in order to assess the long term safety and efficacy of Risankizumab (BI 655066) in patients with plaque psoriasis who have completed the phase 2 trial 1311.2. Moreover, this trial was meant to offer patients continuous treatment with Risankizumab until the marketing approval and availability of Risankizumab in the respective participating countries.

In the course of the acquisition of Risankizumab by Abbvie and the transition of responsibilities from BI to Abbvie it is planned to transfer the patients who are treated in 1311.13 into M15-997 which is sponsored and conducted by Abbvie. M15-997 is an open label extension trial in which patients who have completed one of the Risankizumab pivotal trials in the indication of plaque psoriasis receive 150 mg Risankizumab every 12 weeks.

For patients who discontinue study medication before Extended end of treatment (for any reason), or before approval of this amendment and start to rollover patients to the M15-997 from 01-May-2018 an early Extended EOT visit should be scheduled. If the decision to discontinue study participation is taken at a regular study visit, the visit should be turned into an Extended EOT visit. If the decision to discontinue study participation is taken in between study visits, an Extended EOT visit is to be scheduled at the earliest convenience and by the latest at the next upcoming visit according to the Flow Chart. This early Extended EOT visit will include the same procedures as the normal EOT, and the patient will subsequently enter a follow up period of 12 weeks, until a final Extended EOS visit is performed. If the decision to discontinue is taken in the Extended follow up period, the Extended EOS visit is to be scheduled at the earliest convenience. The procedures described at Extended EOS will be performed and the information will be recorded in the CRFs.

The end of study procedures are listed in [Flow Chart](#).

6.2.3.1 Vital status

In case of early discontinuation, information should be collected to differentiate between patients lost to follow-up (investigator not able to contact the patient despite multiple attempts) versus patients the investigator was able to contact who elected to discontinue study participation for any reason. Patients will be asked to give consent to be contacted (or for their primary care physician to be contacted) by the study team to obtain vital status information preferably at the time of study entry. This consent must be documented in the patient notes. Patient's vital status, including cause of death, will be collected every 12 months from Extended EOS until the last patient completes the regular scheduled Extended EOS. Vital status data will be collected in the eCRFs.

All clinically significant abnormal values (including laboratory parameters) will be followed up using the appropriate tests until a return to a medically acceptable level is achieved. AEs persisting after trial completion must be followed up, until they have normalised or been sufficiently characterised.

7.2 NULL AND ALTERNATIVE HYPOTHESES

The primary hypothesis is that BI 655066 will sustain effectiveness without emergent safety issues during the extended visit period. This will be characterized descriptively. There is no formal statistical hypothesis testing in this study.

7.3 PLANNED ANALYSES

The descriptive analyses will be based on proportions of patients achieving a response (e.g., achieving PASI₉₀, sPGA of clear or almost clear, etc.), Kaplan Meier empirical survival curves to describe patterns of event incidence, and cumulative event rates at critical time-point.

The study is designed to gain as much exposure as possible with adequate documentation of safety, efficacy, and antibody emergence.

For all analyses, baseline refers to the baseline value in the 1311.2 study.

7.3.1 Primary analyses

The achievement of PASI90 at week 48 in the Extended dosing period is the primary efficacy endpoint, which is a binary variable.

For primary safety, the overall incidence rates of AEs, drug related AEs, and SAEs will be calculated.

7.3.2 Secondary analyses

The same methods as discussed for the primary analyses will be used to analyse all binary secondary and other endpoints, which include achievement of PASI50 / PASI75 / PASI90 / PASI100 at all Extended dosing period visits where PASI is collected and achievement of sPGA of clear or almost clear at all Extended dosing period visits where sPGA is collected.

Time to loss of PASI₅₀ / PASI₇₅ / PASI₉₀ / PASI₁₀₀, and time to loss of sPGA of clear or almost clear will be analysed using a Kaplan-Meier estimate.

Percent change from baseline in Pain-VAS for patients with non-zero baseline will be summarized descriptively at time points collected.

DLQI will be summarized descriptively at time points collected.

Additional information on these analyses will be provided in the trial statistical analysis plan.

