2.2 TRIAL OBJECTIVES

The overall purpose of this open label extension (OLE) trial is to assess long-term safety and efficacy (durability of response) of BI 655066 in patients with moderate to severe chronic plaque psoriasis. In addition, this study will provide an opportunity for subjects to have extended access to a proven active therapy for approximately four years administration.

The primary objective of the study is to investigate safety of BI 655066, in patients with moderate to severe chronic plaque psoriasis, receiving long-term treatment.

Additional objectives of this study are to further investigate long-term efficacy, tolerability, pharmacokinetics, pharmacodynamics and immunogenicity of BI 655066.

Study endpoints are listed in [Section 5](#).

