5.1.1.3 Further endpoints of efficacy

Additional efficacy analyses will include, but are not limited to, the following:

- achievement of PASI₅₀ at all Extended dosing period visits where PASI is collected
- achievement of PASI₇₅ at all Extended dosing period visits where PASI is collected
- achievement of PASI₉₀ at all Extended dosing period visits where PASI is collected
- achievement of PASI₁₀₀ at all Extended dosing period visits where PASI is collected
- achievement of sPGA of clear or almost clear at all visits where sPGA is collected
- time to loss of PASI₅₀, which is a time to failure endpoint. This will be repeated using PASI₇₅, PASI₉₀, and PASI₁₀₀ as the endpoint.
- sPGA will be evaluated in terms of time to loss of response which is defined as a score exceeding 1, and will be evaluated as a time to failure endpoint
- change from baseline in Pain-VAS (in subgroup of patients with psoriatic arthritis only where baseline VAS is from 1311.2)
- mean DLQI scores at all Extended dosing period visits where PASI is collected

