### **3.0                   Introduction**

This statistical analysis plan (SAP) describes the statistical analysis to be completed by the AbbVie Clinical Statistics Department for study Protocol M16-009 Amendment 6 dated 30 January 2018.

This SAP will provide details to further elaborate statistical methods as outlined in the Protocol M16-009 and will describe analysis conventions to guide the statistical programming work. The SAP will be signed off before the study database is locked.

Analyses will be performed using SAS® version 9.4 (SAS Institute, Inc., Cary, NC 27513) or higher using the UNIX operating system.

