## **10.0 Efficacy Analysis**

### **10.1 General Considerations**

The efficacy analysis will be performed for ITT population. The efficacy analysis will use the data from this study with baseline from Study 1311.2 and will be summarized by treatment groups in Study 1311.2.

Continuous variables will be summarized by the number of observations, mean, standard deviation, median, minimum, maximum, as well as the 95% confidence intervals (CIs) of the mean values. Categorical variables will be summarized by counts and percentages, as

well as the 95% CIs of the percentages. No statistical tests will be performed in this study.

No missing data imputation will be applied. All efficacy analyses will be based on Observed Cases (OC) analysis, and thus a subject who does not have an evaluation at the analysis time point will not be included.

All endpoints will be analyzed up to the last visit at least one subject has observed measurements of that variable.

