## **10.3 Additional Efficacy Analyses**

The following additional efficacy variables will be summarized at all Extended dosing period visits:

- Proportion of subjects achieving PASI 50/75/90/100
- Proportion of subjects achieving the sPGA score of clear or almost clear
- Change from baseline in Pain-VAS (in subgroup of patients with diagnosed and suspected psoriatic arthritis)
- Change from baseline in DLQI.

- Proportion of subjects achieving DLQI score of 0 and 0/1;

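### The SAP leaves out the protocol's Kaplan-Meier analysis of time to loss of PASI and sPGA response and does not say that it was dropped

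*Protocol*

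**What the plan says.** Time to loss of response appears in five places in the protocol.

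- The synopsis lists it among the statistical methods.
- Section 5.1.1.3 lists it among the further efficacy endpoints, as a time-to-failure variable for PASI 50 that is repeated for PASI 75, 90 and 100. For sPGA it specifies "time to loss of response which is defined as a score exceeding 1".
- Section 7.1 names it in the statistical design.
- Section 7.3 plans "Kaplan Meier empirical survival curves to describe patterns of event incidence", together with cumulative event rates.
- Section 7.3.2 fixes the method: time to loss of the four PASI levels "and time to loss of sPGA of clear or almost clear will be analysed using a Kaplan-Meier estimate". It leaves further detail to the SAP.

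Section 2.2 gives the purpose that this serves: the trial is "to assess long-term safety and efficacy (durability of response) of BI 655066".

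SAP 3.0 sets its own scope: "This SAP will provide details to further elaborate statistical methods as outlined in the Protocol M16-009". SAP 10.1 then says "All efficacy analyses will be based on Observed Cases (OC) analysis", without imputation, using counts, percentages and means with confidence intervals. SAP 10.2 lists proportions at Week 48. SAP 10.3 opens with "The following additional efficacy variables will be summarized at all Extended dosing period visits" and lists proportions and changes from baseline.

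The protocol also plans two safety analyses of the same kind. Time to AESI is in the synopsis, 7.1 and 7.3.3. Time to ADA emergence is in 5.2.1.3, 7.1 and 7.3.3, with Kaplan-Meier named in the synopsis and in 7.3.3.

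**The concern.** The protocol promises a specific analysis of a stated trial purpose and sends the reader to the SAP for the details. The SAP has neither the analysis nor a statement that it was withdrawn, so a reader cannot tell an intended deletion from an oversight.

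By-visit proportions answer a different question: how many of the patients seen at this visit are in response now. They do not follow a patient from response to loss. If the choices that define loss are made after the data have been seen, or the curves are never drawn, the report will describe durability only through net response at each visit.

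**Working it through.** No figure in the plan underlies this point, so there is nothing to recompute. The check is a comparison of the two documents.

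**1. Same trial.** SAP 3.0 cites the study under another number, but the protocol date it gives, 30 January 2018, is that of protocol version 6.0. Its design section also describes the same roll-over from 1311.2.

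**2. Side by side.**

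| Planned in the protocol | Counterpart in the SAP |
|---|---|
| Kaplan-Meier time to loss of PASI 50/75/90/100 (5.1.1.3, 7.3.2) | None; by-visit proportions in 10.2 and 10.3 |
| Kaplan-Meier time to loss of sPGA clear/almost clear (5.1.1.3, 7.3.2) | None; by-visit proportions in 10.2 and 10.3 |
| Time to first AESI onset (synopsis, 7.1, 7.3.3) | None; section 11.2 gives adverse event tables, rates and listings |
| Kaplan-Meier time to ADA (synopsis, 7.3.3) | None; 12.0 excludes pharmacokinetics and does not mention ADA |

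That makes 4 + 1 = 5 efficacy estimates and two safety analyses without a counterpart.

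**3. Not placed elsewhere.** The SAP's contents list has no time-to-event section. Its lists of six tables and three figures contain no such output; the three figures are design diagrams.

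**4. Not declared.** The SAP does announce other departures and exclusions. Section 11.3.2 replaces the laboratory grading scale and gives a reason, 12.0 excludes pharmacokinetics and 13.0 excludes biomarkers. Section 14.0 reports no changes because this is the first version.

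**5. By-visit proportions are no substitute.** Take a group all in response at the start, with a flat proportion in response afterwards and no dropout. If the same patients are below threshold each time, that proportion is also the share that kept its response. If different patients fall below and recover, the share that never lost response is lower, yet the table looks identical. In addition, Observed Cases drops a patient from any visit without an evaluation, whereas Kaplan-Meier uses follow-up until censoring.

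**6. The protocol alone does not settle the analysis.** These choices are open and matter in this trial:

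- *Origin.* Patients may enter after completing 1311.2 (inclusion criterion 1a) and so may already be responders at Extended Visit 1 (EV1). If the clock starts only at EV2, a loss between EV1 and EV2 is not counted. For PASI 90, that is the loss that leads to a dose increase.
- *Off-drug values.* Early discontinuers receive no dose at Extended EOT and return for Extended EOS 12 weeks later (Flow Chart footnotes 4 and 10). If EOT replaces a scheduled dosing visit, EOS falls about 12 + 12 = 24 weeks after the last dose.
- *Stopping for lack of efficacy.* Censoring these patients as if uninformative would flatter durability. SAP 8.0 already reports discontinuation by reason.
- *Restricted medication.* Protocol 3.3.4.1 sets aside efficacy data collected after its use, while 7.4 counts use of inappropriate psoriasis medication as failure. These two passages need reconciling.

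**The case against.** The strongest objection is one of weight. Time to loss is a further endpoint, and protocol 7.1 and 7.2 rule out hypothesis testing. The primary efficacy endpoint and every listed secondary one are in SAP 10.2. On this view one sentence saying that the analysis is dropped would be enough. Most of that stands. It limits the point to a missing description, and a recorded and justified deletion would close it. It does not make silence acceptable, because 7.3.2 commits to the analysis and relies on the SAP to specify it.

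The second objection is that adding curves is not simple. Censoring everyone at the last assessment would mishandle stopping for lack of efficacy and would mix off-drug relapse with on-treatment durability. Curves for many subgroups would go beyond 7.3.2 and be imprecise. This also stands, and the fix below allows for it.

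A reader might infer more than the documents support:

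- *That the by-visit tables are wrong.* They correctly describe net response among patients observed at each visit.
- *That durability will be overstated by some amount.* No loss, regain or dropout rates are given from which to derive one.
- *That the ADA analysis has certainly been abandoned.* ADA sampling and assay sit in the protocol's pharmacokinetic section (5.5), so the exclusion in SAP 12.0 may be meant to cover it.
- *That section 7.3.3 promises Kaplan-Meier for AESIs.* It names time to first onset but no method.

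**Conclusion.** The omission is confirmed on the text. The SAP as written would not produce the five planned Kaplan-Meier estimates of time to loss of response, and it does not say so. Time to first AESI is also missing. Time to ADA is either missing or handled somewhere that the SAP does not name.

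The consequence is limited. No test, primary result or listed secondary endpoint is affected. The loss is a planned description of durability, which is part of the trial's stated purpose and cannot be recovered from the by-visit tables. Its numerical size cannot be given from these documents. The omission should be corrected before lock, but it does not threaten the trial's main results. Nothing shows whether it was deliberate.

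**What to change.** SAP 3.0 places sign-off before database lock, so settle this by then.

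**Efficacy (SAP 10.3).** Add an overall Kaplan-Meier estimate of time to loss for each PASI level and for sPGA clear/almost clear, among patients who have that response.

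- Origin: for example the first Extended dosing period visit with the response, stating whether EV1 responders are included.
- Event: the first later visit without the response (for sPGA, a score above 1).
- Censoring: at the last on-treatment assessment or at transfer to M15-997. Present off-drug Extended EOS values after early discontinuation separately.
- Sensitivity analyses: one counting discontinuation for lack of efficacy as loss, and one requiring loss at two consecutive visits.
- Reporting: numbers at risk and 95% confidence intervals, at time points chosen by the number at risk.
- Reconcile protocol 3.3.4.1 with 7.4 before fixing how restricted medication enters the event.

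SAP 10.1 says that efficacy "will be summarized by treatment groups in Study 1311.2", so state that the main estimate here is overall. Curves by 1311.2 arm or by dose group are optional and descriptive only. With about 100 patients and four arms, equal roll-over (an assumption) would leave 100/4 = 25 per arm. Patients whose dose is increased are below PASI 90 at EV2 by definition, so their PASI 90 curve should not be compared directly with that of patients who stay on 90 mg.

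**Safety (SAP 11).** Add time to first AESI using the definition in protocol 5.2.2.1. Adjudicated MACE in SAP Table 2 covers only cardiovascular death, myocardial infarction and stroke, so use it only as a supplement. Add Kaplan-Meier time to ADA from first risankizumab exposure in either trial, or state where ADA is analysed.

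**If any of these analyses is intentionally dropped,** record that in the SAP with the reason.

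**Cost.** SAP wording, 5 main efficacy estimates, 5 x 2 = 10 sensitivity estimates and the safety outputs. All come from assessments already scheduled, with no change to visits or data collection.
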